#### **5.7.5.4 Vital Signs**

Vital Signs data will be presented in a Listing by Vaccine Group and subject for each parameter using the Safety Population.

#### **5.7.5.5 Physical Examination**

Physical examination will be presented in a Listing for the scheduled visits and which consist of assessments of the planned injection site, spleen & lymph nodes (LN), arm movement and strength and any others.

#### **5.7.5.6 Clinical Laboratory Parameters**

Laboratory evaluation results and changes from baseline will be summarized descriptively by visit using the Safety Population. Unless otherwise specified, all continuous laboratory data will be summarized using descriptive statistics (n, mean, standard deviation (SD), median, minimum, and maximum) for each scheduled study assessment as well as change from baseline and percentage change from baseline [if applicable] by parameter class (hematology and biochemistry).

Hematology, chemistry, rheumatoid factor (RF) and anti-double strand DNA (anti-dsDNA) antibody data will be summarized by displaying shifts from baseline value (Normal/Abnormal) to subsequent assessment after administration of study product.

Safety laboratory data will be listed by visit for each parameter and subject and summarized by Vaccine Group and placebo. All abnormal values that met the definition of an AE as per the protocol will be flagged on the listing.

Hematology parameters includes WBC, Hemoglobin, Platelet Count, Absolute Neutrophil Count and Absolute Eosinophil Count

Biochemistry parameters includes ALT and Creatinine.

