#### 2.3.1.2 Risks of Vaccination

Possible local vaccine reactions include pain, swelling, erythema, induration, transient limitation of limb movement, lymphadenopathy, or pruritus at the injection site. Local subcutaneous nodules, believed to be granulomatous reactions to aluminum hydroxide, have been observed with use of aluminum hydroxide-based adjuvants. Thus, most aluminum hydroxide-adsorbed vaccines are injected intramuscularly rather than subcutaneously. Systemic reactions such as fever, headache, malaise, myalgia, and joint pain, may also possibly occur. Immediate hypersensitivity reactions including urticaria, anaphylaxis, or other IgE-mediated responses are possible as with any vaccine. As with any investigational vaccine, there is a theoretical possibility of risks about which we have no present knowledge. Subjects will be informed of any such risks should further data become available.

Transient, clinically insignificant decreases in white blood cell counts and platelet counts have been observed in the two weeks following receipt of other CpG ODN adjuvant preparations.

CpG 10104 is an immune activator, and has the potential to overcome the normal tolerance of the immune system for self antigens. In a number of murine models, administration of CpG ODN has been associated with development of certain autoimmune phenomenon. However, the relevance of this finding to humans is unclear because while TLR9 receptors are widely distributed among immune cells in mice, they appear to be restricted to B cells and plasmacytoid dendritic cells in humans. No subject in any study to date with CpG 7909 oligonucleotides, a closely related CpG sequence to CpG 10104, has developed signs or symptoms of autoimmune disease.

In animal studies, CpG ODN given by themselves only rarely induce the production of anti-double-stranded DNA antibodies. However, if the CpG 7909 ODN is administered as a complex together with a foreign protein or other antigen that can elicit T cell help, then it is likely that antibodies against the CpG 7909 ODN will be produced, and these may cross-react with double-stranded DNA. Vaccination of humans with a CpG 7909 ODN together with an antigen capable of binding to the ODN could be expected to result in the production of IgG anti-ODN antibodies, which could cross react with self DNA.

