## 5.2 Subject Exclusion Criteria

1. Pregnancy as determined by a positive urine human choriogonadotropin (hCG) test (if female).
2. Subject unwilling to use effective contraception for a minimum of 30 days prior to vaccination and up until documentation of clearance of hookworm infection post-CHHI (if female and not surgically sterile, abstinent from intercourse with a male partner, in a monogamous relationship with a vasectomized partner, at least 2 years post-menopausal, or determined otherwise by medical evaluation to be sterile).
3. Currently lactating and breast-feeding or plans to breastfeed at any given time from the first study vaccination until clearance of hookworm infection post-CHHI (if female).
4. Evidence of clinically significant neurologic, cardiac, pulmonary, hepatic, rheumatologic, autoimmune, gastrointestinal, diabetes, or renal disease by history, physical examination, and/or laboratory studies.

*Includes the conditions and diagnoses defined as AESIs in Section 9.3.4.*

5. Has a diagnosis of schizophrenia, bipolar disease or other major psychiatric condition that would make compliance with study visits/procedures difficult (e.g., subject with psychoses or history of suicide attempt or gesture in the 3 years before study entry, ongoing risk for suicide).
6. Known or suspected immunodeficiency or immunosuppression as a result of an underlying illness or treatment.

*Causes for immunosuppression may include, but are not limited to, poorly-controlled diabetes mellitus, chronic liver disease, renal insufficiency, active neoplastic disease or a history of hematologic malignancy, connective tissue disease, organ transplant.*

7. Laboratory evidence of liver disease (alanine aminotransferase [ALT] greater than 1.25-times the upper reference limit).
8. Laboratory evidence of renal disease (serum creatinine greater than 1.25-times the upper reference limit, or urine dipstick testing positive for glucose or more than trace protein).
9. Laboratory evidence of hematologic disease (hemoglobin <11.1 g/dl [females] or <12.5 g/dl [males]; absolute leukocyte count <3400/mm^3 or >10.8 x 10^3/mm^3; absolute eosinophil count >500/mm^3; or platelet count <140,000/mm^3).

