**Table 5: Assessment of Laboratory Adverse Event Severity**

HEMATOLOGY	Grade 1 (Mild)	Grade 2 (Moderate)	Grade 3 (Severe)
Hemoglobin Males	11.0 – 12.0 g/dL	9.5 – 10.9 g/dL	<9.5 g/dL
Females	10.3 – 11.3 g/dL	8.5 – 10.2 g/dL	<8.5 g/dL
Platelets	110,000 – 130,000/mm 	90,000 – 109,999/mm 	<90,000/mm 
WBCs (increase)	10,800 – 15,000/mm 	15,001 – 20,000/mm 	<20,000/mm 
WBCs (decrease)	2300 – 3200/mm 	1400 – 2299/mm 	<1400/mm 
ANC (decrease)	750 – 1000/mm 	500 – 749/mm 	<500/mm 
Absolute eosinophil count (increase)	700 – 1500/mm 	1501 – 5000/mm 	>5000/mm 
CLINICAL CHEMISTRIES	Grade 1	Grade 2	Grade 3
Serum creatinine	1.5 – 1.7 mg/dL	1.8 – 2.0 mg/dL	>2.0 mg/dL or requires dialysis
ALT Males	58 – 115 U/L	116 – 230 U/L	>230 U/L
Females	64 – 128 U/L	129 – 255 U/L	>255 U/L

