## **9.5 Halting Rules**

If the study vaccine or CHHI is considered significantly reactogenic or results in significant AEs (see below and **Section 9.2**), additional vaccinations or CHHIs will be suspended until reviewed by the SMC, Independent Safety Monitor, DMID Medical Monitor, and IND sponsor (BCM). Any recommendation of the Independent Safety Monitor, DMID Medical Monitor, and SMC to resume or suspend further injections or CHHIs (either for an individual subject or the full study) will be communicated in writing to the sponsor and Principal Investigator. All communications from the SMC will subsequently be forwarded by the investigators to the IRB.

The following criteria will be used to define significant reactogenicity:

- One or more participants experience a protocol defined SAE that is determined to be possibly, probably, or definitely related to a study vaccine or CHHI, **OR**,
- One or more participants experience a protocol defined AESI that is determined to be possibly, probably, or definitely related to a study vaccine or CHHI, **OR**,
- One or more participants experience a protocol defined Grade 3 hypersensitivity reaction that is possibly, probably or definitely related to a study vaccine or CHHI, **OR**,
- Two or more participants experience a protocol defined Grade 2 hypersensitivity reaction that is probably or definitely related to a study vaccine or CHHI, **OR**,
- Three or more participants experience the same objective physical finding or laboratory abnormality of Grade 3 or higher (with the exception of isolated Grade 3 erythema or swelling at the site of vaccination or Grade 3 erythema and/or rash at the site of application of the larvae), that is determined to be probably or definitely related to a study vaccine or CHHI, **OR**,
- Three or more participants experience the same Grade 2 or higher safety laboratory abnormality (excluding eosinophilia [or increased white blood cell count secondary to eosinophilia] after CHHI) or Grade 3 clinical AE that is possibly, probably or definitely related to a study vaccine or CHHI.

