### **5.2 Definition**

**Baseline:** Baseline is defined as the latest non-missing assessment (whether from scheduled or unscheduled) prior to the first dose administration of the study vaccine, unless otherwise stated.

The **Post-baseline** values are defined as measurements taken after the first administration of study product.

**Change from Baseline:** The change from baseline values will be calculated as post baseline value minus the baseline value.

**An Adverse Event** is any untoward medical occurrence in a subject or clinical investigation in a subject administered a pharmaceutical product and which does not necessarily have to have a causal relationship with this vaccination. An adverse event can be any unfavorable sign (including an abnormal laboratory finding), symptom, or disease temporally associated with the use of the investigational product, whether considered related or not related to the investigational product.

A pre-vaccination condition is any event in a clinical study subject that occurs after he/she signed the Informed Consent Form (ICF) up until the first administration of study vaccine. All pre-vaccination conditions will be considered as medical history whereas any pre-vaccination condition that worsens after vaccination will be considered as an AE.

**An SAE** is any AE that results in death, is life-threatening (this refers to an event in which the subject was at risk of death at the time of the event; it does not refer to an event that hypothetically might have caused death had it been more severe), requires inpatient hospitalization or prolongation of existing hospitalization, results in persistent or significant disability/incapacity, is a congenital anomaly/birth defect, requires medical or surgical intervention to prevent any of the occurrences noted above.

**Unexpected Adverse Event:** Any adverse event, the specificity or severity of which is not consistent with the current Investigator's Brochure.

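### Normal/Abnormal laboratory shift tables cannot show the direction or grade of a change, and shifts after challenge have no pre-challenge reference

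*SAP*

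**What the plan says.** SAP 5.7.5.6 specifies one shift display for all laboratory parameters: hematology, chemistry, RF and anti-dsDNA "will be summarized by displaying shifts from baseline value (Normal/Abnormal) to subsequent assessment after administration of study product". It names no Low/High split and no grade. It does not say whether Normal refers to the laboratory's reference range or to the limits in Protocol Table 5, nor whether the later assessment is each visit, the last or the worst.

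The starting point comes from SAP 5.2: "Baseline is defined as the latest non-missing assessment (whether from scheduled or unscheduled) prior to the first dose administration of the study vaccine". That definition allows exceptions, but SAP 5.7.5.6 makes none for the challenge phase.

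The protocol treats laboratory change in more detail. Table 5 grades WBC increases and decreases on separate rows and grades hemoglobin in three steps by sex. Protocol 2.3.1.2, on the two weeks after other CpG preparations, says: "Transient, clinically insignificant decreases in white blood cell counts and platelet counts have been observed". Protocol 9.5 sets aside the opposite change in one halting criterion: "excluding eosinophilia [or increased white blood cell count secondary to eosinophilia] after CHHI".

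**The concern.** The protocol anticipates opposite white-cell changes from its two exposures, lower after CpG and higher with eosinophilia after challenge. It also expresses laboratory safety in grades. A halting criterion in 9.5 counts Grade 2 or higher abnormalities, hemoglobin worse than Grade 1 after challenge is an AESI (9.3.4), and a Grade 3 value that does not improve can hold back a vaccination or the challenge (5.3.3). A shift table is normally where a reader sees, per arm, how many subjects moved, which way and how far. Here it answers only whether they left an undefined normal range.

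The reference point adds a second problem. A shift seen after challenge is measured from before the first vaccination, so the table cannot separate what was already present on the day of challenge from what came later.

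At stake is the clarity of the per-arm laboratory summary. No efficacy result depends on it, and the halting criteria do not operate through this table.

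**Working it through.** The plan states no figure to reproduce here. The check sets the SAP's categories against the protocol's own limits.

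**1. What two states merge.** In steps 1 and 3, Abnormal is read as any Table 5 grade.
- WBC has 7 Table 5 states: three grades low, ungraded, three grades high. A full shift table has 7 × 7 = 49 cells; Normal/Abnormal has 2 × 2 = 4.
- Hemoglobin has 4 states (ungraded, Grades 1 to 3), so 4 × 4 = 16 cells against 4.
- For hemoglobin, Normal to Abnormal pools 3 transitions (to Grade 1, 2 or 3). Abnormal to Abnormal pools 3 × 3 = 9, of which 3 are worsening (1 to 2, 1 to 3, 2 to 3).

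**2. White-cell direction.** A count of 2,000/mm³ lies in 1,400–2,299, a Grade 2 decrease. A count of 12,000/mm³ lies in 10,800–15,000, a Grade 1 increase. Both also lie outside the entry limits of 3,400 and 10,800 (Protocol 5.2). On either set of limits in the documents, both code as Abnormal.

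**3. Which cells will be used.** Entry limits (Protocol 5.2) set against Table 5 Grade 1:

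| Parameter | Eligible at screening | Grade 1 range | Overlap |
|---|---|---|---|
| Hemoglobin, male (g/dL) | ≥12.5 | 11.0–12.0 | none |
| Hemoglobin, female (g/dL) | ≥11.1 | 10.3–11.3 | 11.1–11.3 |
| WBC, low (/mm³) | 3,400–10,800 | 2,300–3,200 | none |
| WBC, high (/mm³) | 3,400–10,800 | 10,800–15,000 | exactly 10,800 |
| Platelets (/mm³) | ≥140,000 | 110,000–130,000 | none |
| Eosinophils (/mm³) | ≤500 | 700–1,500 | none |

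Almost every subject is therefore ungraded at screening on these parameters. A Day 0 draw, which the SAP baseline would use, could add a few graded starts. The usual loss is in the Normal to Abnormal cell, where Grade 1 and Grade 3 look the same.

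**4. The reference point after challenge.** Vaccinations fall on Days 0, 56 and 112 and challenge on Day 140. Appendix A shows cumulative blood volumes of 94 mL at Day 0 and 604 mL at Day 126, so 604 − 94 = 510 mL is scheduled in between. A post-challenge shift from the Day 0 baseline mixes vaccination, blood sampling and infection. Protocol 7.3 already schedules hematology and biochemistry on Day 140 ahead of larval application, so a pre-challenge value exists.

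**5. Where direction and grade survive elsewhere in the SAP.**
- By-visit summaries with change from baseline (5.7.5.6): direction and size, but not how many subjects changed.
- Laboratory adverse events by organ class and preferred term (5.7.5.1): counts per arm, with no severity named.
- Adverse events by severity (5.7.5.1): highest grade, without the baseline-to-worst transition.
- AESI table (5.7.5.1): post-challenge anemia above Grade 1, but not smaller falls, WBC or platelets.
- By-visit listing with flags (5.7.5.6): every value, but not a per-arm summary.

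**The case against.** The strongest reply is that little is lost overall. The primary laboratory outcome is the frequency of laboratory adverse events, which has its own table. With 12 subjects per arm, the listing lets a reader see every value. CpG-related decreases and challenge-related increases fall in different periods, so they are confused only if the shift table pools visits. SAP 5.7.5.6 opens by describing summaries by visit, and the table list is a separate document (SAP 10) that may say more. Most of this stands, and it limits the point to the shift tables. It does not remove it: even within one visit, low and high counts share a category, as do Grade 1 and Grade 3.

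A reader might infer more than the documents support:
- **That direction and grade disappear from the laboratory analysis.** They do not; the five outputs in step 5 carry much of both.
- **That a woman falling from 11.2 to 8.4 g/dL (2.8 g/dL, Grade 1 to Grade 3) goes unseen.** This needs a baseline in the narrow 11.1–11.3 band, or a lower Day 0 value, and a definition of Normal that excludes it. If 11.2 counts as Normal, the shift shows. After challenge, 8.4 g/dL would also be an AESI.
- **That graded shifts would catch a man falling from 15.5 to 12.1 g/dL (3.4 g/dL).** Male Grade 1 begins at 12.0, so he is Grade 0 to Grade 0. Normal/Abnormal would show him only if he crossed whatever limit defines Normal. The by-visit change summaries cover such falls.
- **That blood loss is the main harm of challenge.** Protocol 2.3.1.3 names skin and gastrointestinal effects as expected and places anemia with longer-lasting infection.
- **That the two-state coding makes post-challenge rates track infection.** Any post-challenge laboratory summary would do so, including a graded one.

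**Conclusion.** The point holds for the shift tables. As specified, they cannot show direction or grade for hematology and chemistry, and shifts after challenge have no pre-challenge reference. The merging of low and high white cells follows from the stated two-state rule under either set of limits in the documents. The pooling of Grades 1 to 3 assumes that Abnormal includes all graded values, which the SAP leaves open. Whether the vaccination and challenge periods are also pooled is unsettled.

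This is a modest weakness in reporting a safety outcome, partly offset by other planned outputs. Efficacy is unaffected. It is worth correcting because the data are already scheduled and the change is small.

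**What to change.** In SAP 5.7.5.6:
- For hematology and chemistry, replace Normal/Abnormal with shifts in Table 5 grade (0 to 3), with WBC increase and decrease shown separately.
- Present two periods: from the pre-first-dose value to the worst value in the vaccination phase, and from the last pre-challenge value (Day 140) to the worst value after challenge. For ALT and creatinine, Protocol 7.3 schedules only Day 154 after challenge, so the worst value is that one plus any unscheduled result.
- Keep the by-visit change-from-baseline summaries, which cover hemoglobin falls that stay within Grade 0. A per-arm count of hemoglobin falls by size is an optional supplement.
- Keep Normal/Abnormal for RF and anti-dsDNA, which Table 5 does not grade, and state which limits define Normal.
- Before programming, have the sponsor reconcile the Table 5 Grade 3 entry for WBC increase, printed as <20,000/mm³, with the Grade 2 range beside it (15,001–20,000/mm³). The two overlap as printed and cannot be programmed.

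The cost is a few more table shells and some programming, with no new data. Cells will be sparse with 12 subjects per arm. In the vaccination-phase tables for the parameters in step 3, the entry limits should leave most subjects in the Grade 0 starting row, which keeps those tables readable.

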#### **6. INTERIM ANALYSES**

Not Applicable

#### **7. CHANGES OF ANALYSIS FROM PROTOCOL**

The analysis point no. 2 in the analysis plan section secondary outcome #2 and #3 measures performs the ANOVA. Hence analysis Section “e” (Protocol Version 4.0 Page no.72) is not required if it is not specific to three-way ANOVA.

